4.2.2 Secondary efficacy analysis

The secondary efficacy data are:

- Change from baseline of NRS-11 pain intensity after 4 weeks of treatment
- Proportion of patients with the NRS-11 pain intensity reduction of ≥30% versus baseline during at least 50% of treatment weeks over treatment period
- Proportion of patients with the NRS-11 pain intensity reduction of \geq 50% versus baseline during at least 50% of treatment weeks over treatment period.
- Proportion of patients with the abdominal pain assessed in the Patient Dairy completely resolved during at least 50% of treatment days over treatment period (NRS-11 0 assessment).
- Change from baseline of NRS-11 bloating/flatulence intensity after 4 weeks of treatment
- Proportion of patients with the NRS-11 bloating/flatulence intensity reduction of \geq 30% versus baseline during at least 50% of treatment weeks over treatment period.
- Proportion of patients with the NRS-11 bloating/flatulence intensity reduction of \geq 50% versus baseline during at least 50% of treatment weeks over treatment period.
- Proportion of patients with the bloating/flatulence assessed in the Patient Dairy completely resolved during at least 50% of treatment days over treatment period (NRS-11 0 assessment).
- Change in number of days per week during study treatment period when drotaverine was taken.
- Change in quality-of-life evaluation using IBS-QOL questionnaire versus baseline.

Secondary endpoints "Change from baseline of NRS-11 pain intensity after 4 weeks of treatment", "Change from baseline of NRS-11 bloating/flatulence intensity after 4 weeks of treatment" and "Change in quality-of-life evaluation using IBS-QOL questionnaire versus

baseline" will be compared between the two treatment groups by means of analysis of covariance (ANCOVA), with treatment, site as fixed effects and baseline value (if available) as covariate. The same SAS code with MIXED procedure as for primary endpoint will be used for these endpoints.

Secondary endpoint "Change in number of days per week during study treatment period when drotaverine was taken" will be compared between the two treatment groups by means of analysis of variance (ANOVA), with treatment, site as fixed effects. To achieve full conformity with ANCOVA in case of missing's the ANOVA analysis will be performed using MIXED procedure as well:

The baseline abdominal pain and bloating/flatulence intensity will be determined as the average of daily episodes NRS-11 assessment during 7 days before randomization (last week of screening and run-in period, in other words, the average of daily episodes from - 6 to 1 days). The data from the last week of screening and run-in period will be also used for baseline assessment of stool frequency and consistency and number of days of drotaverine intake. Week 1 (average of data 2 - 8 days), Week 2 (average of data 9 - 15 days), Week 3 (average of data 16 - 22 days) and Week 4 (average of data from the last 7 days of the corresponding week in the case duration of treatment 28 days: 23 to 29 days or data from the last 7 days before the last treatment day inclusively in the case duration of treatment did not equal 28 days).

The proportion of patients with the *Scale* reduction of $\geq A\%$ versus baseline during at least 50% of treatment weeks over treatment period must be calculated as:

$$\frac{n_T}{N_T}$$

where N_T is total number of patients in the treatment arm T, n_T is number of patients in the treatment arm T who had reduction of $\ge A\%$ versus baseline (week 0) during at least 2 of treatment weeks over treatment period: week 1, week 2, week 3, week 4). Reduction of $\ge A\%$ must calculate as:

$$Reduction_{i} = \frac{\overline{Scale_{Week_{i}}} - \overline{Scale_{Week_{0}}}}{\overline{Scale_{Week_{0}}}} \times 100 \ge A\%$$

The transformation formula used for the IBS-QOL total and scale scores is:

 $Score = \frac{The sum of the items - lowest possible score}{Possible raw score range} \times 100$

Where

lowest possible score = number of questions \times lowest possible score of the items

possible raw score range

= number of questions

 \times (upper possible score of the items - lowest possible score of the items)

The comparisons of treatment arms for secondary endpoints with "Proportion of patients with the..." type will be analyzed using Fisher exact test. The test will be performed by separately for for Mebeverine + Simethicone combination VS Duspatalin (mebeverin) and Mebeverine + Simethicone combination VS Espumisan (simethicone) comparisons.

Fisher exact test will be performed using following SAS code for the analysis:

```
PROC FREQ DATA = [dataset name];
  weight [frequency var] / ZEROS;
  tables [frequency var lvl 1/ frequency var lvl 2] * [Arm] / exact Fisher;
RUN;
```

If SAS code produces the "Row or column sum zero. No statistics computed for this table." output due to insufficient memory available to complete the Fisher exact computations, then the p-value should be assumed as equal 1.0000.

Source: NST002 – NST004, NSL010, NSL011, NSL012, NSL003, NSL014, NSL015.

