5.2. Administration of the study drug and randomization

At the visit 2 Week 0, Day 1, all eligible patients will be randomized into three equal groups (1:1:1):

- Mebeverine+Simethicone, 135 mg+80 mg, three times a day during 4 weeks
- Duspatalin® 135 mg three times a day during 4 weeks
- Espumisan®, 80 mg three times a day during 4 weeks

Patients will take the study drugs during 4 weeks: Mebeverine+Simethicone 1 tablet three times a day before meal, Duspatali® 1 tablet three times a day before meal, Espumisan ® 2 capsules 3 times a day after or before meal.

The last dose has to be taken at the evening before the Visit 3 (Week 4, Day 29).

The patients will register the study drug administration in the diary.

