7.2.3. End of treatment (Visit 3, Week 4, Day 29)

Visit window ± 1 day

- Assessment of AE and concomitant medication
- Measuring, weight, BMI
- Physical examination

Confidential Page 65 of 94

- Assessment of vital signs
- Blood sampling for safety laboratory tests (hematology and blood chemistry)
- Urine collection for urinalysis
- Patient diary assessment (daily data for 4 weeks, including abdominal pain and bloating/flatulence intensity, stool consistency in line with the Bristol stool scale, stool frequency, drotaverine intake and menstrual bleeding days)
- Evaluate the quality of life (IBSQOL questionnaire)
- Study drug return, accountability and compliance assessment

At this point the period of the study therapy is completed. The patient will be given recommendations for further treatment as part of standard therapy

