9.7.3. Secondary efficacy end points

- Change from baseline of NRS-11 pain intensity after 4 weeks of treatment
- Proportion of patients with the NRS-11 pain intensity reduction of ≥30% versus baseline during at least 50% of treatment weeks over treatment period
- Proportion of patients with the NRS-11 pain intensity reduction of $\geq 50\%$ versus baseline during at least 50% of treatment weeks over treatment period.
- Proportion of patients with the abdominal pain assessed in the Patient Dairy completely resolved during at least 50% of treatment weeks over treatment period (NRS-11 0 assessment).
- Change from baseline of NRS-11 bloating/flatulence intensity after 4 weeks of treatment
- Proportion of patients with the NRS-11 bloating/flatulence intensity reduction of ≥30% versus baseline during at least 50% of treatment weeks over treatment period.
- Proportion of patients with the NRS-11 bloating/flatulence intensity reduction of \geq 50% versus baseline during at least 50% of treatment weeks over treatment period.

Confidential Page 69 of 94

- Proportion of patients with the bloating/flatulence assessed in the Patient Dairy completely resolved during at least 50% of treatment weeks over treatment period (NRS-11 0 assessment).
- For patients with constipation: proportion of patients with any increase in number of CSBM per week versus baseline during at least 50% of treatment weeks.
- For patients with diarrhea: proportion of patients with any decrease in the number of days per week with at least one stool consistency of Type 6 or Type 7 BSS versus baseline during at least 50% of treatment weeks.
- Change in number of days per week during study treatment period when drotaverine was taken.
- Change in quality of life evaluation using IBSQOL questionnaire versus baseline.

The baseline abdominal pain and bloating/flatulence intensity will be determined as average of the worst daily episodes NRS-11 assessment during 7 days before randomization (last week of screening and run-in period). The data from last week of screening and run-in period will be also used for baseline assessment of stool frequency and consistency and number of days of drotaverin intake. Week 1, Week 2, Week3 and Week 4 assessments are the same (data from the last 7 days of the corresponding week).

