9.9. Procedures to record missing, not subject to analysis and dubious data

No missing data will be added. To analyze the efficacy endpoints the last observation carry forward (LOCF) will be used. To determine the sensitivity of the evaluation: first the patients with

Confidential Page 70 of 94

missing data will be analyzed, then the patients will be analyzed without replacing the missing data.

[figure not shown]

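### SAP 4.2.2 judges complete resolution by days where the protocol and SAP 3.3 say weeks, reverses the sign of the reduction formula, and gives no analysis of two stool endpoints or of secondary endpoints by subgroup

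*SAP*

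**What the plan says.** **Complete resolution.** SAP 4.2.2 gives the same rule for pain and for bloating/flatulence: "completely resolved during at least 50% of treatment days over treatment period (NRS-11 0 assessment". Protocol 9.7.3 has "completely resolved during at least 50% of treatment weeks over treatment period (NRS-11 0 assessment", and the SAP's own objectives in 3.3 also use weeks. The neighboring endpoints for 30% and 50% reduction stay on weeks in both documents. For those, SAP 4.2.2 turns half of the weeks into a count: "during at least 2 of treatment weeks over treatment period: week 1, week 2, week 3, week 4".

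**Stool endpoints.** Protocol 9.7.3 includes one endpoint for patients with constipation (CSBM per week) and one for patients with diarrhea (days with Bristol type 6 or 7 stools). Neither appears in SAP 3.3 or 4.2.2, and SAP 5.3 names only NRS-11 scores as efficacy data. SAP 4.2.2 still defines a stool baseline, and the visit table in SAP 6.1.5 still schedules stool frequency and the Bristol scale.

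**Subgroups.** Protocol 2.2 and 9.4 plan secondary endpoint analyses in six subgroups. SAP 4.3.1 uses these groups for baseline characteristics, and the supplied SAP does not mention them elsewhere.

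**Formula.** SAP 4.2.2 calculates percentage reduction as (Week i − Week 0) / Week 0 × 100 and requires the result to be at least A%.

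**The concern.** The SAP contradicts the protocol and also itself on what a complete responder is. A programmer cannot satisfy SAP 3.3 and 4.2.2 together. If 4.2.2 is followed, two secondary endpoints are reported under the protocol's name with a different rule. Two others have no responder rule or test, and no subgroup has a planned efficacy result, so parts of the protocol's secondary objectives would go unanswered. The formula, taken literally, selects patients who get worse for the four endpoints on 30% and 50% reduction.

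**Working it through.** The plan states no figure on this point that could be reproduced. The check compares the texts and then works out what each rule does.

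1. **Endpoint count.** Protocol 9.7.3 lists 12 secondary efficacy endpoints and SAP 4.2.2 lists 10. The difference, 12 − 10 = 2, is the two stool endpoints. Of the 10 that remain, 2 have moved from weeks to days. Subgroups with a planned secondary endpoint analysis: 6 in the protocol, 0 in the supplied SAP.

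2. **Day rule against week rule, complete diary.** Inputs: 28 diary days (SAP Days 2 to 29) and four separate 7-day weeks. Neither document defines a resolved week; I read it as a weekly mean of 0. Scores cannot be negative, so a mean of 0 means seven zeros. Two resolved weeks give 2 × 7 = 14 zero days, and 14/28 = 50%. Every week responder is therefore a day responder. The reverse fails: six zero days in each week give 24/28 = 86% of days and no resolved week.

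3. **Where that ordering can break.** Protocol 5.2 says "The last dose has to be taken at the evening before the Visit 3 (Week 4, Day 29"), and Protocol 7.2.3 allows "Visit window ± 1 day". A visit on Day 28 puts the last dose on Day 27. Treatment then did not last 28 days, so SAP 4.2.2 takes for Week 4 the "data from the last 7 days before the last treatment day inclusively in the case duration of treatment did not equal 28 days", that is Days 21 to 27. Week 3 is Days 16 to 22, so Days 21 and 22 count twice. A patient with zeros on Days 16 to 27 only has Weeks 3 and 4 resolved and meets the week rule, yet has 12/26 = 46% zero days and fails the day rule. Missing days can break the ordering as well.

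4. **Size, for illustration only.** With independent days and a common probability p of a zero score, the day rule gives P(Bin(28, p) ≥ 14) and the week rule P(Bin(4, p^7) ≥ 2). At p = 0.5 these are 57.5% and 0.04%; at p = 0.8, about 100% and 19.6%; at p = 0.95, about 100% and 91.5%. Real days cluster. In the table each patient has an own p from the stated distribution, and each day repeats the previous day's status with probability rho, otherwise it is redrawn with probability p of a zero (exact calculation; day rule vs week rule, %).

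| Assumed p | rho 0 | rho 0.5 | rho 0.8 | rho 0.95 |
|---|---|---|---|---|
| Beta(1,9), mean 0.10 | 0.7 vs <0.1 | 1.8 vs 0.1 | 5.3 vs 2.7 | 9.4 vs 8.8 |
| Beta(1,2), mean 0.33 | 27.6 vs 2.5 | 28.9 vs 7.7 | 31.3 vs 20.6 | 33.4 vs 32.0 |
| Beta(0.5,0.5), mean 0.50 | 51.1 vs 23.6 | 51.1 vs 31.7 | 50.9 vs 42.5 | 50.5 vs 49.4 |

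5. **Missing days.** For Beta(1,2) and rho 0.8, with 10% of days missing at random, the simulated week-rule rate is 20.3% if daily scores are carried forward, but 7.8% if all seven days must be recorded. The rule used has to be written down.

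6. **Sign.** A fall from 6 to 3 gives (3 − 6)/6 = −50%, which fails a 50% threshold. A rise from 6 to 9 gives (9 − 6)/6 = +50%, which passes.

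**The case against.** Several counter-arguments have force.

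- **The absences may not be real.** Module 2, the table shells and some SAP text are not in the supplied copy, and SAP 4.2 promises descriptive statistics for every planned efficacy endpoint. Protocol 9.10 asks that changes be identified, but does not say the SAP must explain them. This stands so far that one cannot say the stool tables will not be produced, only that the supplied text specifies no analysis. The descriptive promise covers no responder rule, between-group test or subgroup. The days and weeks conflict lies wholly within supplied text.
- **The sign is a slip in notation.** The surrounding words say reduction, and few programmers would code it literally. That is fair, but it is a specification formula and costs nothing to correct.
- **The size rests on invented rates.** This stands. Entry requires weekly mean scores of 4 to 9 for both symptoms, which makes frequent zero days less obvious. In the low-rate row the gap stays under 3 points. The textual conflict needs no simulation.
- **Missing data are not unaddressed.** Protocol 9.9 says "To analyze the efficacy endpoints the last observation carry forward (LOCF) will be used", SAP 4.2 uses available data and LOCF, and SAP 4.2.1 carries the nearest earlier post-baseline value forward. This stands, although none of these says whether a daily score or a weekly mean is carried, and the last ends with an ALT response that is no endpoint here.
- **Special fixed windows would not help.** In the overlap example, carrying forward fills Days 28 and 29 with zeros, so Week 4 is still resolved. These endpoints would also get a different Week 4 from the other weekly endpoints. I therefore propose none.

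A reader might infer that the day rule was chosen to flatter the combination, or that it biases the comparison. The documents do not support this: the same rule applies to all three arms, and nothing shows a motive or a between-arm effect.

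**Conclusion.** The SAP is wrong as written, for secondary endpoints only. The two complete-resolution endpoints are defined by days in SAP 4.2.2 against weeks in Protocol 9.7.3 and SAP 3.3, and the reduction formula is reversed against its own wording. The supplied SAP gives no analysis of the two stool endpoints and no subgroup analysis of secondary endpoints, and does not identify these as changes. They may be deliberate, or covered in material not supplied.

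The day rule is never stricter under three conditions: a complete diary, weeks that do not overlap, and a resolved week meaning a weekly mean of 0. It should not be called more lenient in every case. How much more lenient it is cannot be known from the documents. The illustrative gaps depend on the assumed frequency and clustering of zero days and are neither estimates nor bounds. The primary endpoint, sample size, type I error and criterion for trial success are untouched.

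**What to change.** - In SAP 4.2.2, change days to weeks for both complete-resolution endpoints. Define a resolved week as a weekly mean NRS-11 of 0, and a responder as at least 2 of Weeks 1 to 4, with the same week windows as the other weekly endpoints. Show any day-based version only as a labelled supplementary analysis.
- For missing days, refer to the existing LOCF text in Protocol 9.9 and SAP 4.2 and 4.2.1, and say that it applies to the daily scores if that is meant.
- Correct the formula to (Week 0 − Week i) / Week 0 × 100.
- Restore the type 6/7 endpoint; Protocol 6.9 has the Bristol type recorded for every bowel movement. Restore the CSBM endpoint if completeness and spontaneity were recorded; the diary contents in Protocol Table 1 mention only stool frequency and Bristol type.
- Restore the six-subgroup analyses of secondary endpoints as estimates with confidence intervals and no confirmatory claims, and state how patients are assigned to the bowel-habit groups.
- Alternatively, identify each dropped or redefined item as a change from the protocol, with its reason, in line with Protocol 9.10.

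No new data collection is needed. The cost is SAP wording, one or two stool tables and a sizeable set of subgroup tables: 10 endpoints × 6 subgroups × 2 comparisons = 120 estimates before any stool endpoint, some on small counts. Complete-resolution rates will probably be lower than under the day rule.

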3.2. Screening and run-in period

3.2.1. Visit 1 (Week -1, Day -7, for colonoscopy patients Week -3, Day -21)

After signing the Patient Information Leaflet and the Informed Consent Form, screening procedures will be performed, including collection of demographic data and medical history, physical examination, height and body weight measurements, BMI determination, vital signs assessment, sampling of biological material for hematology and biochemistry blood tests, urinalysis, test for fecal calprotectin. For patients older than 50 Error! Bookmark not defined. vears old who have not had a colonoscopy conclusion in the last 12 months prior to screening which confirms the absence of significant pathological changes, this procedure will be performed as part of the screening examination. Screening period will be prolonged for 2 more weeks (up to 3 weeks) for these patients. Colonoscopy should be performed not later than 10 days before the randomization visit. Assessment of abdominal pain and bloating/flatulence intensities will be performed using an 11-point Numeric Rating Scale (NRS-11). An ECG and urine pregnancy test for women of childbearing potential will be performed. The drotaverin intake drotaverin intake not more than 80 mg 1 - 3 times a day during one day after pain episode will be allowed for intensiveabdominal pain during the study; No-spa® will be recommended to the patients for this purpose. Other drugs for abdominal pain and bloating/flatulence treatment will be prohibited. Any changes in diet and probiotic therapy (including drug and dose regimen changes) will be also prohibited.

Patients will be given Patient Diaries for daily self-assessment of abdominal pain, bloating/flatulence severity with NRS-11 (the most severe episode during last 24 hours), study drug and drotaverin intake, stool frequency and consistency with Bristol Stool Chart (BSC). Women with childbearing potential will register menstrual bleeding days.

At the end of the Screening and Run-in period, patients will be invited to the center to assess the abdominal pain and bloating/flatulence intensities and confirm compliance with the inclusion/exclusion criteria. The baseline abdominal pain and bloating/flatulence intensity for the inclusion/exclusion criteria assessment will be determined as average daily NRS-11 abdominal pain and bloating/flatulence score during last week of screening period (7 days before randomization).

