9.7.4. Secondary efficacy end points analysis

Intergroup comparisons will also be performed for secondary efficacy endpoints using the χ^2 /Fisher exact test and 95% confidence intervals for differences in proportions will be given. Additionally, the proportion of patients with reduced severity of pain in the bowel region and bloating/flatulence during each week of the 4-week treatment period charts will be constructed.

ANCOVA model, which will include treatment and site as fixed effect, and baseline value as covariate, will be used for continuous covariates comparison presenting treatment effect estimates and associated 95% CIs.

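### The SAP drops the baseline covariate for change in drotaverine days, against the protocol's ANCOVA and although a run-in baseline is collected

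*SAP*

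**What the plan says.** Protocol 9.7.4, repeated in the synopsis, gives one model for continuous secondary comparisons: "ANCOVA model, which will include treatment and site as fixed effect, and baseline value as covariate, will be used for continuous covariates comparison". It makes no exception for rescue use.

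SAP 4.2.2 applies that model to pain, bloating/flatulence and IBS-QOL, "with treatment, site as fixed effects and baseline value (if available) as covariate". The next paragraph treats drotaverine days differently: this endpoint "will be compared between the two treatment groups by means of analysis of variance (ANOVA), with treatment, site as fixed effects". Baseline is not among the terms. The SAP adds that PROC MIXED will be used here too, so that missing values are handled as in the ANCOVA. It does not say why the covariate was removed.

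Protocol 9.7.3 words the endpoint as "Change in number of days per week during study treatment period when drotaverine was taken". Both documents define a baseline for it. Data from the last run-in week are "used for baseline assessment of stool frequency and consistency and number of days of drotaverin intake" (Protocol 9.7.3), and SAP 4.2.2 says the same: "used for baseline assessment of stool frequency and consistency and number of days of drotaverine intake". Under Protocol 3.2.1, patients record drotaverine intake in the diary from Visit 1.

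**The concern.** The SAP defines a baseline for this endpoint and then names a model that does not adjust for it. A change score is tied to its own baseline. Patients with heavy run-in use tend to fall back towards the mean, and a patient with no run-in drotaverine days cannot improve. Leaving baseline out of a change-score analysis keeps that variation in the residual and lets a chance difference in run-in use move the treatment comparison.

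This is the only listed efficacy endpoint that measures rescue use, and the rescue drug is itself an antispasmodic. In an open-label trial with patient-reported outcomes, readers will use it to judge whether a pain difference could reflect differing rescue use. A needlessly wide interval makes that check weaker. Protocol 9.10 also asks that changes from the protocol's methods be identified, and this one is not.

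**Working it through.** **The plan's own figure.** The plan states no variance, correlation or power for drotaverine days. The only sized endpoint is the primary one (Protocol 9.2: difference 1.0, SD 2.5, two-sided alpha 0.05, power 90%). The fixed-sample formula gives n = 2 × (1.960 + 1.282)² × 2.5² / 1.0² ≈ 131.3, so 132 per group, as stated. That figure does not bear on this point and is used below only as the arm size.

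**Notation.** Let r be the correlation between run-in and on-treatment drotaverine days, and k the SD on treatment divided by the SD at run-in. Neither is in the documents, so both are varied as assumptions. In units of the run-in variance:

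- Residual variance, change score without baseline: k² + 1 − 2rk
- Residual variance, ANCOVA with baseline: k²(1 − r²)
- The first minus the second is (1 − rk)², which is never negative. ANCOVA is therefore never less precise in large samples, and the two are equal only when rk = 1, that is, when the slope on baseline is 1.
- Shift of the unadjusted change estimate per day of baseline imbalance: rk − 1

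**Equal SDs (k = 1).** The variance ratio is (1 − r²) / [2(1 − r)] = (1 + r)/2.

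| r | Variance ratio, ANCOVA / ANOVA on change | CI width ratio (square root) | Extra patients ANOVA needs for equal precision | Shift from a 0.5 day/week imbalance, 0.5 × (1 − r) |
|---|---|---|---|---|
| 0.3 | 0.65 | 0.81 | 54% | 0.35 day |
| 0.5 | 0.75 | 0.87 | 33% | 0.25 day |
| 0.7 | 0.85 | 0.92 | 18% | 0.15 day |

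The shift runs against the imbalance: the arm with more run-in use appears to improve more.

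**Unequal SDs.** Variance ratios at r = 0.3, 0.5 and 0.7:

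- k = 0.5: 0.24, 0.25, 0.23
- k = 0.75: 0.46, 0.52, 0.56
- k = 1.25: 0.78, 0.89, 0.98

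**Simulation with site effects.** Two arms of 132 patients were spread over 45 sites fitted as fixed effects, with k = 1, normal data and 1,500 replicates per value of r. The variance ratios were 0.66, 0.79 and 0.89 at r = 0.3, 0.5 and 0.7, close to the formula and slightly above it. Regressing the estimate on the baseline imbalance gave slopes of −0.70, −0.45 and −0.26 for the ANOVA and 0.01, 0.05 and 0.03 for the ANCOVA.

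**If the outcome is on-treatment days with nothing subtracted.** The endpoint title does not say from baseline, so this reading is possible. The ANCOVA/ANOVA variance ratio is then 1 − r² = 0.91, 0.75 and 0.51 at the same values of r. Adjustment gains precision on either reading. With baseline in the model, the treatment estimate is the same whether or not baseline is subtracted from the outcome.

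**The case against.** The strongest reply is that little depends on this. Drotaverine days is one of ten secondary efficacy endpoints in SAP 4.2.2, it was not sized, and success is decided by the two primary comparisons alone. Randomisation keeps the ANOVA on change unbiased on average and its type I error valid. All of that stands. The cost is in precision and in sensitivity to a chance imbalance in the sample actually drawn.

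The size of the gain is also uncertain. The outcome is a count from 0 to 7 that may pile up at zero, and it may be averaged over several weeks. The SDs need not be equal, and the gain could be close to nil or well above the equal-SD figures. This stands too, and is why the range is shown. It gives no reason to omit the covariate, because any skewness affects the planned ANOVA equally.

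The protocol delegates detail to a SAP finalised before database lock, so a change is allowed. What remains is that it is neither flagged nor explained. The missing reference to baseline in the endpoint title might explain the different treatment, but both documents then define a baseline for this variable.

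One caveat: the SAS code announced for this model was absent from the text available for this review, so the point rests on the sentence that names the model terms. If the code contains a baseline term, that sentence should be corrected instead.

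**Conclusion.** The concern holds. For one secondary endpoint the SAP departs, without explanation, from the protocol's model and leaves unused a baseline that it defines itself. Under equal SDs and r between 0.3 and 0.7, including baseline would cut the variance by 35% to 15% and narrow the confidence interval by 19% to 8%. It would also essentially remove a shift of 0.35 to 0.15 day per week for each 0.5 day of chance run-in imbalance. These sizes rest on assumed values of r and the SD ratio. The direction does not: in large samples the adjusted analysis is never less precise. The primary conclusion of the trial is not affected. The change should be made because it restores the protocol's model at almost no cost.

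**What to change.** In SAP 4.2.2, move the drotaverine endpoint into the ANCOVA sentence and use the same PROC MIXED model as for the other continuous secondary endpoints: change in drotaverine days per week = treatment + site + run-in drotaverine days per week. Report the combination-versus-mebeverine and combination-versus-simethicone differences, each with a 95% confidence interval, as Protocol 9.7.4 requires. In the same edit, state which on-treatment value enters the change (Week 4 or the average over the four weeks), since neither document says.

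If the sponsor prefers to keep the ANOVA, the SAP should record it as a departure from Protocol 9.7.4, give the reason, and add the ANCOVA as a sensitivity analysis.

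The cost is a sentence or two in the SAP and one model term, using one degree of freedom. No new data are needed.
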